Post-discharge hospital utilization, i.e., readmissions and ED visits, represent a costly failure of medical care, especially among diabetic patients.[11-13] Patients with diabetes represent about 9% of the US population,[14] but they account for 23% of hospitalizations (over 8 million per year).[15, 16] The number and proportion of hospitalized patients with diabetes has increased steadily over the past two decades,[15, 17, 16] mirroring the increasing incidence and prevalence of diabetes in the general population.[18, 19, 14] While the overall 30d readmission rate is 8.5-13.5%,[20, 21] the 30d readmission rate of diabetic patients is 14.4-21.0%.[22-25] In 2012, costs associated with the hospitalization of diabetic patients in the US were \$124 billion of which an estimated \$25 billion was attributable to 30d readmissions.[26, 27, 15] ED visits of patients with diabetes also impose significant costs to health systems.[28] Reducing 30d readmissions among diabetic patients has the potential to greatly reduce healthcare costs. **A modest 5% reduction in the 30d readmission rate would result in 82,754 fewer admissions per year, translating into an estimated annual cost savings of \$1.2 billion.**[26, 16] Starting October 1, 2012, the Centers for Medicare and Medicaid Services decreased payments to hospitals that have greater-than-expected 30d readmission rates, reflecting an effort to improve care while reducing costs.[29] These data and the widespread interest in healthcare reform have prompted recent calls for more research on how to prevent 30d readmissions in this important group of patients.[30-32]

Identifying and intervening in the highest risk diabetic patients to reduce readmission rates may have a large impact. Such an approach, colloquially known as “**medical hot-spotting,**” has been successfully applied in a socioeconomically disadvantaged population to reduce hospital utilization in

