We estimate that 25% of screened patients will not meet eligibility criteria, which means that at least 300 patients will be screened.

d) Study Timelines

Subjects will be enrolled during their hospital stay and will participate in the study for 3 months following hospital discharge. The intervention will be delivered during the 4 weeks following discharge. Final assessment for outcomes will be performed at 3 months after discharge. We anticipate enrollment will occur between July and December of 2019. We estimate that primary analyses will be completed by June of 2020.

e) Study Endpoints

The primary outcome will be the number of initial hospital readmissions within 30 days of discharge. Secondary outcomes will also be assessed at 30 days of discharge unless otherwise specified. Secondary outcomes will include:

1. time to first readmission
2. number of emergency department (ED) visits
3. a composite of 30d readmissions and ED visits

Readmission Pilot Trial

4. number of primary care and specialist provider follow-up visits scheduled and attended
5. incidence of medication review or reconciliation post-discharge
6. cost of post-discharge care as a sum of ED visits, readmission, home health services, and outpatient provider visits
7. cost of the intervention
8. subject experience assessed by a brief questionnaire
9. self-monitored blood glucose levels and frequency of testing
10. change in well-being from baseline to 5 weeks after discharge as measured by the World Health Organization Well-Being Index (WHO-5).[43]
11. change in diabetes-related distress at 5 weeks after discharge as measured by the Problem Areas in Diabetes (PAID) scale.[44]
12. change in perceived social support at 5 weeks after discharge as measured by the Multidimensional Scale of Perceived Social Support (MSPSS).[45]
13. change in perceived stress at 5 weeks after discharge as measured by the perceived stress scale (PSS).[46]
14. change in diabetes knowledge at 5 weeks after discharge as measured by the Diabetes Knowledge Test (DKT2).[47]
15. change in A1c level from baseline to 3 months after the index discharge

f) Procedures Involved in the Human Research

After enrollment, subjects will be sorted into 2 groups based on the predicted risk of readmission by the DERRI: high risk and low risk (Figure 1).

[figure not shown]

Figure 1. Allocation of study participants

Low-risk group:

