4) Post-discharge support: At 24 to 48 hours post-discharge, a nurse Navigator will call the patient to assess the patient’s status, confirm receipt of and compliance with medications, verify the follow-up appointment schedule, assess for barriers to following the discharge plan, determine the need for a community health worker (CHW) referral, and review blood glucose control (patients who are discharged on non-insulin regimens will be expected to test their blood glucoses at least once a day, and patients who are discharged on an insulin regimen will be expected to test their blood glucoses at least twice a day). Similar phone calls will be made weekly for four weeks following discharge by a Navigator. If a patient reports significant high or low blood glucose levels, then the PI or a co-Investigator (Endocrinologists) will call the patient to adjust diabetes therapy (See Tables 1a and 1b for insulin dose adjustment protocols). Eligible patients will receive a referral for a nursing visit from a local home care agency to assess medical needs for support at home and medication reconciliation. Referral to a CHW may be made if subjects are found to have non-medical needs and/or obstacles to maintaining self-care and attending follow-up appointments. Such non-medical support might include transportation to and from medical appointments, food, housing, or legal assistance, relief from utility bills, verification of insurance, support groups and delivery of durable medical equipment.

Table 1a. **Outpatient basal insulin dose adjustment:**

Basal Insulin	
If mean FBG > 180 mg/dL for the last 2 consecutive days and no episodes of hypoglycemia	Increase daily basal dose by 4 IU
If mean FBG > 140 mg/dL for the last 2 consecutive days and no episodes of hypoglycemia	Increase daily basal dose by 2 IU
If mean FBG between 100 to 140 mg/dL for the last 2 consecutive days and no episodes of hypoglycemia	No Change
If any FBG between 70 – 99 mg/dl	Decrease by 4 IU or 10% of total daily basal dose
If any FBG < 70 mg/dl	Decrease by 8 IU or 20% of total daily basal dose
If any FBG < 40 mg/dl	Decrease total daily basal dose by 30%

FBG=Fasting blood glucose; Hypoglycemia=typical symptoms (e.g., sweating, tremor, acute hunger, anxiety) and/or blood glucose <70 mg/dL

Table 1b. **Outpatient prandial/pre-meal insulin dose adjustment based on subsequent mealtime/HS BG values:**

Pre-meal Rapid Insulin		
Pre-meal Dose, U	BG 70 – 100 mg/dl*	BG 141-180 mg/dl**

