≤ 10 U	Decrease by 1 U	Increase by 1 U
>11- 19 U	Decrease by 2 U	Increase by 2 U
≥ 20 U	Decrease by 3 U	Increase by 3 U
Pre-meal Dose, U	BG 40-70 mg/dl x 1	BG 180-240 mg/dl x 1

Readmission Pilot Trial

≤ 10 U	Decrease by 2 U	Increase by 2 U
>11- 19 U	Decrease by 3 U	Increase by 3 U
≥ 20 U	Decrease by 4 U	Increase by 4 U
Pre-meal Dose, U	BG < 40 mg/dl x 1***	BG > 240 mg/dl x 1
≤ 10 U	Decrease by 4 U	Increase by 3 U
>11- 19 U	Decrease by 6 U	Increase by 4 U
≥ 20 U	Decrease by 8 U	Increase by 5 U

Pre-meal insulin dose adjustment is based on the subsequent BG value, e.g., pre-breakfast insulin dose is based on the pre-lunch BG.

* If > ½ of the mealtime/HS BG values for the week were below target.

**If > ½ of the mealtime/HS BG values for the week were above target.

*** Decrease by 30-40% in the event of severe hypoglycemia (mealtime/HS BG < 40 mg/dl).

BG=blood glucose; Mealtime/HS=pre-lunch, pre-dinner, or bedtime

The above algorithm provides recommended insulin doses and may be modified based on clinical judgment of the investigator or co-investigator.

Usual care: Most aspects of the intervention go above-and-beyond usual care. Patients in the usual care group will receive the standard discharge instructions and medication reconciliation process. Those who are new to diabetes receive training by a floor nurse on using a glucometer as well as a stock set of printed educational materials. The floor nurses also train patients who are new to insulin injections as needed. Patients with diabetes are referred to outpatient diabetes education at Temple on a case-by-case basis as determined by the primary hospital provider team. Diabetes therapy upon discharge is decided on a case-by-case basis by the primary team. Discharge instructions are routinely sent to the primary care physician either by fax or EPIC. Most TUH patients receive a phone call 2 to 4 days after discharge from a CHW that includes checking on the status

Table 2. Timeline for assessments of subjects

Visit #	1	2	3	4	5	6	7	8
Time (weeks)	0	2 days	1	2	3	4	5	13
Intervention group								
Phone call/clinic visit								X
Psychometric assessments	X							X
Diabetes knowledge	X							X
30d endpoints								X
Interview							X	
A1C	X							X
Navigator call		X	X	X	X	X		
Blood glucose		X	X	X	X	X	X	
Adverse events		X	X	X	X	X	X	
Usual care group								
Phone call								X
Psychometric assessments	X							X
Diabetes knowledge	X							X
30d endpoints								X
A1C	X							X
Blood glucose								X

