Adverse events								X
Low-risk group								
Chart review/phone call								X
Psychometric assessments	X							X
Diabetes knowledge	X							X
A1C	X							X
30d endpoints								X

Readmission Pilot Trial

of follow-up appointments, confirming access to medications, and answering questions.

Data collection: The following data will be collected at baseline: A1c, sociodemographics, medical history, including HIV, substance abuse, and mental health status, which are likely risk factors for admission, relevant laboratory results, admission diagnoses, self-reported goals for health and diabetes, well-being (WHO-5), diabetes-related distress (PAID scale), perceived social support (MSPSS), perceived stress (PSS), diabetes knowledge (DKT2), depression screening by the PHQ-2/9, and health literacy by the BHLS (Table 2).

The following data will be collected during follow-up: A1c, discharge diagnoses, hospital readmission (date, primary diagnosis), ED visits (date, primary diagnosis), physician follow-up appointments scheduled and/or attended, post-discharge medication reconciliation (yes/no), cost of post-discharge care, self-monitored blood glucose levels, Nurse Navigator time to deliver the intervention (minutes), well-being (WHO-5), diabetes-related distress (PAID scale), perceived social support (MSPSS), perceived stress (PSS), diabetes knowledge (DKT2), depression (PHQ), and patient experience according to a brief questionnaire (**Appendix Item 3a [usual care] or 3b [intervention]**). These follow-up data will be collected during a phone call about 5 weeks after the index discharge. Baseline and 3-month post-discharge A1c levels will be obtained as part of standard-of-care. A letter reminding patients to do the 3-month blood draw for the A1c test will be sent by mail.

Data will be collected by phone interviews with subjects and review of the electronic medical record (EMR). The Research Specialist will be primarily responsible for screening and recruiting subjects, data collection and data entry.

Phase B: Qualitative evaluation of intervention

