All data collected by the research team will be considered part of the participant's confidential record. Data collected on paper from research participants will be placed in a locked file cabinet in the GCRC within 24 hours. The destruction date of paper files will be at least 7 years from the termination of the study and will be authorized by the PI. Access to research and confidential records will be limited to clinical investigators and research coordinators.

h) Data Management

Statistical analysis: Distributions of the data will be assessed by descriptive statistical and graphical methods. To assess the randomization procedure, baseline values of all variables will be compared between the intervention and usual care group. Between-group differences for continuous variables will be compared using the Wilcoxon test. Proportions will be compared between groups using the chi-square test or exact tests when expected cell counts are less than 5. The primary outcome of 30d readmission rate will be compared between intervention and control groups with the chi-square test. Point estimates of 30d readmission rates will be obtained and presented with 95% confidence intervals. Time to readmission will be estimated by Kaplan-Meier curve and compared between groups by log-rank test. The composite of 30d readmission and ED visits will be compared by Cox regression model. Continuous secondary outcomes will be compared using Wilcoxon test. Categorical secondary outcomes will be compared using chi-square test. The primary analyses for all outcomes will be performed in the intention-to-treat (ITT) population. Secondary analyses for all outcomes will be performed in a per-protocol population restricted to subjects who complete at least one follow-up phone call. In addition, outcomes will be assessed for differences by the number of follow-up phone calls

Readmission Pilot Trial

completed (dose-response analysis). Lastly, all outcomes will be assessed in the ITT subgroup of subjects with a baseline A1c >7%. Statistical significance will be claimed at an alpha level of 0.05.

Power analysis: The sample size for Phase 2A was based on an expected drop-out and post-enrollment exclusion rate of 25% as well as the capacity of the research team. Because this is a pilot feasibility trial, the study is not powered to detect a difference in outcomes.

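### The dose-response analysis counts calls made during the same 30 days as readmission, so more calls can look protective when they have no effect

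*Protocol*

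**What the plan says.** The statistical analysis paragraph (Protocol, section 8 h) follows the intention-to-treat and per-protocol analyses with: "In addition, outcomes will be assessed for differences by the number of follow-up phone calls", and the sentence ends "completed (dose-response analysis"). So the exposure is the number of completed calls, it applies to all outcomes, and it carries a causal label. The paragraph sets the significance level at 0.05 and does not exempt this analysis.

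The calls are described in section 8 f), under post-discharge support. The first comes 24 to 48 hours after discharge, and then "Similar phone calls will be made weekly for four weeks following discharge by a Navigator". Table 2 marks the same five times: 2 days and weeks 1 to 4.

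The outcome is defined in section 8 e): "The primary outcome will be the number of initial hospital readmissions within 30 days of discharge". The last call, at about day 28, therefore still lies inside the outcome window.

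The protocol does not say whether calls continue, pause or stop when a patient is back in hospital. The analysis sentence contains no landmark, no cut-off at the event and no time-dependent count.

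**The concern.** A dose-response analysis assumes that the dose comes before the response. Here both build up over the same 30 days. A patient readmitted on day 6 may miss the day-7 call because of the admission, and is then recorded as a readmission with a low dose. The low count is a result of the readmission, not its cause.

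This is not a question of power. Low power hides real effects, whereas this mechanism produces false ones in a single direction, that of more calls and fewer readmissions. Aim 1 includes exploring efficacy, and the pilot is preparation for a definitive trial. A significant gradient by number of calls could easily be read as evidence that call intensity drives benefit.

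**Working it through.** The protocol gives no figure for this analysis, so there is nothing to reproduce. The check asks how often the analysis as written would be significant if calls had no effect at all.

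**Inputs from the protocol**
- Calls at about days 2, 7, 14, 21 and 28 (section 8 f and Table 2).
- Intervention arm of 60 (section 8 c), or 60 × 0.75 = 45 after the 25% drop-out and exclusion in the power paragraph.
- Readmission risk: section 5 says "the 30d readmission rate of diabetic patients is 14.4-21.0"%. No figure is given for the DERRI high-risk group.
- Alpha 0.05, taken as two-sided.

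**Assumptions**
- Each call is completed independently with probability 0.5, 0.7 or 0.9.
- A readmission lasts 3, 5 or 7 days.
- After readmission, calls are unaffected, missed only during the stay, or stopped.

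**Model**
- Time to readmission is exponential with hazard −ln(1 − p)/30. For p = 0.21 this is 0.2357/30 = 0.00786 per day, and 60 × 0.21 = 12.6 readmissions are expected.
- The test is the trend test of readmission on call count, significant when N·r² > 3.841.

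**Hand check of the mechanism**
- With a 5-day stay and readmission spread evenly over 30 days, the day-2 call can fall in the stay for 2 possible readmission days and each of the other four calls for 5.
- Expected calls falling in the stay: (2 + 4 × 5)/30 = 0.73. At 70% completion, 0.73 × 0.7 = 0.51 calls are lost.
- Patients not readmitted complete 5 × 0.7 = 3.5 calls on average; readmitted patients complete 3.5 − 0.51 = 2.99.

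**Share of null trials with p < 0.05 (n = 60, risk 21%)**

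| Calls after readmission | Completion 0.5 | 0.7 | 0.9 |
|---|---|---|---|
| Unaffected | – | 5% | 5% |
| Missed during a 3-day stay | 9–10% | 17–18% | – |
| Missed during a 5-day stay | 17–18% | 34–35% | 82% |
| Missed during a 7-day stay | – | 58% | 98% |
| Stop at readmission | – | 99% | 100% |

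Where a range is shown, it covers repeated runs. Whenever calls are missed, essentially all rejections are in the protective direction.

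**Other settings, 5-day stay**
- Risk 14.4%, n = 60: about 27% at 0.7 completion (14–71% over completion 0.5 to 0.9).
- Risk 21%, n = 45: about 27% (14–70%).

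**What the reader would see (risk 21%, 5-day stay, 0.7 completion)**
- Readmission is 33% among patients with 0–2 calls and 14% among those with 4–5, although everyone has the same 21% risk.

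**Time-aligned alternatives under the null**
- Cox regression on calls completed before the event, and a day-7 landmark, each reject in about 4 to 5.5% of trials.

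**The case against.** - **The text is brief.** It does not say that calls after a readmission count, and a statistical analysis plan that counted calls up to the event would not contradict it. That is true. But the protocol fixes the exposure, the outcomes and the dose-response label, and following it as written gives the biased count.
- **The premise is not stated.** If readmission does not affect calls, there is no artefact. This stands, and it is why the result is conditional. The condition is mild, though: the calls cover medication receipt, appointments and home glucose testing, and missing them only during the stay is enough.
- **The size depends on the test and the inputs.** The trend test is an assumption; the protocol names chi-square for categorical outcomes. A chi-square across call counts 0 to 5 (5-day stay, 21% risk) rejects in about a fifth of trials at 0.7 completion and in under a tenth at 0.5. Varying stay and completion together widens the trend-test range to roughly 9–98%. This makes the size less certain but does not remove the bias.
- **The stakes are limited.** The protocol names the Phase B interviews and the team's experience as the guide to the next trial, and says the pilot is not powered. This also stands, and the point concerns an additional analysis only.
- **The alternatives have little power.** With a true 30% hazard reduction per completed call (n = 60, baseline risk 21%, 0.7 completion), the Cox test detects it in about 11% of trials and the landmark in about 9%. That is a reason to present the result as exploratory, not to keep a count that the outcome itself can change.

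**Conclusion.** The concern holds. As written, the dose-response analysis lets readmission reduce the dose it is compared with. With calls missed only during a 5-day stay, about one null trial in three would show a significant protective trend (60 patients, 21% risk, 70% completion, trend test). Depending on what happens to calls after readmission, the figure runs from the nominal 5% to 99%. Completion, length of stay and the call rule are assumptions. The direction of the bias does not depend on them once any calls are missed because of readmission.

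The composite of readmission and ED visits inherits the problem through its readmission component; ED-only visits were not simulated. The primary intention-to-treat comparison is untouched. The per-protocol set, which needs only one completed call, is hardly affected by this mechanism if calls resume after the stay (20.9% instead of 21% in the intervention arm) and moderately if they stop (18.3%). The point is worth fixing before analysis, but it does not threaten the main result.

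**What to change.** For readmission and the readmission/ED composite, replace the comparison by number of calls completed with wording such as: *Within the intervention arm, dose-response will be explored by Cox regression with the number of Navigator calls completed before the event as a time-varying covariate.* An alternative is a day-7 landmark: calls completed by day 7 against events after day 7, among patients still event-free. Label either one exploratory and non-randomised, because patients who answer calls may differ in other ways.

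**Cost.** The change is to the analysis wording. Both versions need the date of each completed call; dates of readmissions and ED visits are already collected (section 8 f, Data collection). The Cox version keeps all events. The landmark discards readmissions before day 7: under a constant hazard at 21% risk, (1 − e^(−0.00786 × 7))/0.21 = 0.0535/0.21, or about 25%, which is about 3 of 13 readmissions at n = 60, and more if readmissions cluster early. The landmark also reduces the dose to 0, 1 or 2 calls, so the Cox version answers the question more fully.

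### The protocol claims significance at 0.05 without tying the claim to the primary outcome or the ITT population, across many outcomes and analyses in a trial it says is not powered

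*Protocol*

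**What the plan says.** Section 8(e), Study Endpoints, names one primary outcome: "The primary outcome will be the number of initial hospital readmissions within 30 days of discharge". It then numbers 15 secondary outcomes, ending with "change in A1c level from baseline to 3 months after the index discharge".

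Section 8(h), Statistical analysis, gives the primary outcome its own test: "The primary outcome of 30d readmission rate will be compared between intervention and control groups with the chi-square test". It makes ITT the primary analysis for all outcomes and adds three further analyses:
- per-protocol: "Secondary analyses for all outcomes will be performed in a per-protocol population restricted to subjects who complete at least one follow-up phone call";
- a dose-response analysis by number of follow-up calls completed;
- all outcomes again in the ITT subgroup with baseline A1c above 7%.

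The paragraph closes with the claim rule: "Statistical significance will be claimed at an alpha level of 0.05". The Power analysis paragraph that follows says: "Because this is a pilot feasibility trial, the study is not powered to detect a difference in outcomes".

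**The concern.** The closing sentence is a rule about what will be claimed, and it comes at the end of a paragraph covering every outcome and every analysis. It is not limited to the primary outcome or to ITT, and the other analyses are not labelled exploratory. Someone following it literally would call any p-value below 0.05 significant, wherever it arose.

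That fits this trial badly. Aim 1 in section 4 is to explore feasibility, acceptability and efficacy, and the protocol disclaims power for outcome differences. What is at stake is how the results are read: an isolated chance finding on a secondary outcome, in a subgroup or in the dose-response analysis could be reported as a demonstrated effect, with the protocol's own wording as authority.

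**Working it through.** **Is there a plan figure to reproduce?** No. The protocol states a per-test alpha of 0.05 but no familywise error rate and no power calculation. Sample size rests on 25% loss and team capacity (60 randomised per arm × 0.75 = 45).

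**Step 1: count the outcomes.** 1 primary + 15 secondary = 16. Two of these do not clearly give a between-arm comparison:
- Item 7, "cost of the intervention", has no usual-care counterpart, which leaves 15.
- Item 8, subject experience, uses arm-specific forms (section 8(f), Data collection: "Appendix Item 3a [usual care] or 3b [intervention"), which leaves 14 if the forms are not comparable.

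I carry 14 and 16 as the limits.

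**Step 2: count the analyses.** There are three overlapping populations (ITT, per-protocol, A1c >7% subgroup) plus one dose-response analysis.

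**Step 3: primary outcome in ITT.** One test at 0.05, so the false-positive chance is 5%.

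**Step 4: all ITT outcomes, if independent.** The chance of at least one p<0.05 under no effect is 1 − 0.95^k.
- k = 14: 1 − 0.95^14 = 0.512; expected false positives 14 × 0.05 = 0.70.
- k = 15: 1 − 0.95^15 = 0.537; expected 0.75.
- k = 16: 1 − 0.95^16 = 0.560; expected 0.80.

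**Step 5: allow for correlation.** The outcomes are related, so independence overstates the chance. I simulated test statistics Z_j = √ρ·G + √(1−ρ)·E_j, with G and E_j standard normal, and counted a hit when any |Z_j| exceeded the two-sided 5% limit. The protocol gives no ρ, so the values are assumed. It does not state sidedness either; I took two-sided.

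**Step 6: add the other analyses.** A subset holding a fraction f of the ITT information has a statistic correlated √f with the ITT statistic. I assumed f = 0.85 to 0.95 for per-protocol and 0.60 to 0.80 for the A1c subgroup. The dose-response statistic was taken as independent of the between-arm statistics.

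Chance of at least one p<0.05 under no effect:

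| Assumed ρ | ITT, 14 outcomes | ITT, 16 outcomes | Three populations, 14–16 outcomes | Plus dose-response, 14–16 outcomes |
|---|---|---|---|---|
| 0 | 51.2% | 56.0% | 68.3–80.0% | 84.5–91.1% |
| 0.3 | 43.8% | 47.6% | 60.1–71.1% | 77.6–84.9% |
| 0.5 | 34.8% | 37.4% | 49.2–59.5% | 66.9–74.6% |
| 0.7 | 24.9% | 26.3% | 35.9–43.9% | 51.9–58.7% |

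**Step 7: the primary outcome alone, if a hit in any analysis counted.** About 8–10% over the three populations, and 12–14% with dose-response added.

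**A caution on dose-response.** Table 2 schedules Navigator calls only in the intervention group, and the number completed is not randomised. The calls fall in the same weeks in which readmission is counted, so a readmitted patient may complete fewer. An association could then appear with no treatment effect. The last column treats this analysis as having a clean 5% error and may understate the chance of a misleading hit.

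**The case against.** The strongest reply is that 0.05 is a conventional level, and that multiplicity detail commonly sits in a statistical analysis plan. The protocol also has a hierarchy: one primary outcome with its own test, 15 outcomes called secondary, ITT as the primary analysis and per-protocol as a secondary one. Aim 1 is worded as exploration. All of this is fair, and it protects the primary ITT test, which keeps its 5%. It does not settle the point, because the claim sentence is something the protocol states and is not linked to that hierarchy.

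The second reply is that a chance finding is not likely in the primary analyses. This stands in part. ITT alone reaches even odds only when the outcomes are nearly independent. Readmission, time to readmission and the composite share events, so some correlations may be high: at ρ = 0.8 the ITT figure is about 20–21%. Exceeding 50% throughout ρ = 0 to 0.7 requires counting the per-protocol, subgroup and dose-response results as well.

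Several stronger readings are tempting, but the documents do not support them:
- A reader might multiply 16 outcomes by four analyses and treat the product as independent tests: 1 − 0.95^64 = 96%. The populations overlap, the outcomes are related, and not all 16 can be compared between arms. That is an upper bound, not a realistic figure.
- A reader might infer that a single hit makes the trial positive. The protocol does not say so.
- A reader might infer that lack of power inflates false positives. It does not raise type I error; it makes a significant result less credible and a non-significant one uninformative.
- A reader might infer that a chance result would shape the definitive trial. Section 8(f), Phase B, ties the future proposal to the interview findings, and team experience to the procedures manual. No p-value is made a decision input.

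**Conclusion.** The point holds as a wording defect with real consequences for interpretation, not as a flaw in the primary test. Followed literally, the claim rule carries a 5% false-positive chance for the primary ITT comparison. With no treatment effect, it gives about a 25–48% chance of at least one significant label among the ITT outcomes at correlations of 0.3 to 0.7 (51–56% if independent), and about 52–91% over everything planned at correlations of 0 to 0.7. The correlations, the overlap fractions and the independence of the dose-response statistic are all assumptions; the protocol gives none of them. The conclusion does not depend on the exact value, since an unrestricted claim sits poorly with an exploratory aim and a statement of no power anywhere in these ranges. It is a cheap improvement.

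**What to change.** Replace the alpha sentence in section 8(h) with one that does two things:
- limits any claim of statistical significance to the primary outcome, 30-day readmission, in the ITT population;
- says that all secondary outcomes, and all per-protocol, dose-response and A1c-subgroup results, will be reported as estimates with 95% confidence intervals, labelled exploratory, with no claim of significance.

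Under that rule the chance of a false claim is 5%. No alpha adjustment, extra patients or dropped analyses are needed. For comparison, sharing 0.05 across the ITT outcomes by Bonferroni would need 0.05/16 = 0.0031 per test (0.05/14 = 0.0036), which would serve little purpose in a pilot. The cost is one sentence and the loss of the significant label on secondary results. As the trial is not powered even for the primary outcome, making no significance claim at all would also be consistent with its purpose.
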